**Clinical Study Protocol**  
**Johnson & Johnson Vision Care, Inc.**

Visit 4: Treatment 2 Follow-Up (after 14h)			
Step	Procedure	Details	
4.15	Exit Visual Acuity	Record distance high contrast LogMAR visual acuity (OD, OS and OU) with their with their refractive correction from Part 1, Visit 1 (or habitual spectacles) in place.	Eurolens Research SOP # 12a
4.16	End of Visit 4 and instructions	Part 1 complete. Subjects will be asked to return for Part 2 between 9-90 days later. Subjects must return to their habitual lenses for at least 7 days (and ideally have a period of 24 hours without lenses) before going ahead with the next study visit.	

**PART 2, VISIT 5**

Subjects must have returned to their habitual lenses for at least 7 days prior to taking part in Part 2. Subjects should also be asked to attend this visit without their habitual lenses *in situ*. If possible subjects should not wear lenses for 24 hours prior to the study visit in order to reduce the risk of biomicroscopic signs being a cause of exclusion to continuing on the study.

The visit can still go ahead if the subject is wearing their habitual lenses and can take place at any time of the working day.

Visit 5: Treatment 3 Lens Fitting and dispensing			
Step	Procedure	Details	
5.1	Adverse Events and Concomitant Medications Review	Review any changes to the subject's medical history or concomitant medications from the previous study visit. Record any changes, and any adverse events.	
5.2	Entrance Visual Acuity	Record distance high contrast LogMAR visual acuity (OD, OS and OU) with their refractive correction from Part 1, Visit 1 (or habitual spectacles), in place.	Eurolens Research SOP # 12a
5.3	Slit lamp biomicroscopy	Grades will be scored to the nearest 0.1 in the best judgment of the investigator using Efron Grading Scales.	Eurolens Research SOP #13
5.4	Continuance	If any slit lamp findings are Efron Grade 3 or greater (e.g. corneal oedema, corneal neovascularization, tarsal abnormalities, conjunctival injection) or < Efron Grade 3 which in the investigator's opinion would contraindicate contact lens wear, the subject may not continue at this time.	

**Clinical Study Protocol**  
**Johnson & Johnson Vision Care, Inc.**

Visit 5: Treatment 3 Lens Fitting and dispensing			
Step	Procedure	Details	
		If in the opinion of the investigator the subject may be eligible at a later date, the subject may be brought in for up to ONE additional visit of this type.	
5.5	Lens application	
An Acuvue Oasys 1-Day contact lens (8.5 mm base curve) will be applied to each eye. BVP and lot number will be recorded. If a lens is damaged, a Product Quality Complaint Form will be completed. The lens will be stored in a labeled vial with unpreserved saline, and clearly differentiated from any other lenses.
 
Lenses will settle for 5 minutes
	
5.6	Lens fitting and surface assessment	
Lens fit will be recorded according to a -2 to +2 integer scale for each of the following criteria: horizontal centration, vertical centration, movement and coverage.
 
The lens surface will be recorded according to the following integer scales: lens deposits (0-2), deposit degree (0-4), lens debris (0-4) and lens wettability (0-4).
 
If the investigator feels that an 9.0 mm base curve lens would provide a better fit, the lens may be changed. If the lens is changed to an 9.0 mm base curve, then the comfort, VA and over-refraction and lens fit assessment should be repeated.
	Eurolens Research Grading Scale (lens fit and surface assessment)
5.7	LogMAR visual acuity & over-refraction	
Distance high contrast visual acuity will be measured for each eye as well as binocularly before and after over-refraction.
 
If there is an over-refraction of +/- 0.50DS or more, the lenses would usually be changed. However, the final decision on this will rest with the investigator. Up to TWO power modifications are allowed.
	Eurolens Research SOP # 12a

**Clinical Study Protocol**  
**Johnson & Johnson Vision Care, Inc.**

Visit 5: Treatment 3 Lens Fitting and dispensing		
Step	Procedure	Details
		Any new lens should be allowed to settle for 5 minutes before comfort is recorded.
5.8	Subjective comfort	Subjective comfort scores for each lens (OD and OS) separately using a vertical VAS scale will be recorded.
5.9	Continuance	
The lens fit and VA must be acceptable in order for a subject to be considered eligible.
 
N.B Minimum acceptable logMAR VA is 0.18 binocularly.
 
If subject is deemed to be ineligible after baseline, proceed to Final Evaluation and complete all forms.

5.10	Dispense lenses	
The subject will be instructed to wear the lenses on a daily disposable basis and informed that no other products should be used until the next study visit. Subjects will be instructed to wear their lenses for at least 5 days per week for about 12 hours per day before the next visit.
 
A patient instruction guide will be issued. Subjects should also be instructed to return any unopened lenses to the investigator at the next visit. Subjects do not need to keep any worn lenses.

5.11	End of Visit 5 and Instructions	Subject discharged and asked to return two weeks later, having worn the study lenses for 6 ±1 hours that day.

**PART 2, VISIT 6**

Subjects will be asked to attend Visit 6 wearing the study lenses. The visit should take place 6 ± 1 hours after the subject applied their lenses on the visit day.

Visit 6: Treatment 3 Follow-Up (after two weeks)		
Step	Procedure	Details
6.1	Adverse Events and Concomitant Medications Review	Review any changes to the subject's medical history or concomitant medications from the previous study visit. Record any changes, and any adverse events.

**Clinical Study Protocol**  
**Johnson & Johnson Vision Care, Inc.**

Visit 6: Treatment 3 Follow-Up (after two weeks)			
Step	Procedure	Details	
6.2	Wearing Time	Record the wearing time on the day of the visit as well as the average wearing time and comfortable wearing time since the last visit.	
6.3	Compliance	Ensure the subject has been wearing lenses for $6 \pm 1$ hours.  If the subject has not been complaint with wearing time, the subject can be asked to return on ONE more occasion.	
6.4	Subject Reported Ocular Symptoms	Record subject reported ocular symptoms.	
6.5	Collection of unopened study lenses	The investigator will collect any unopened lenses.	
6.6	CLDEQ-8	Subjects will complete the CLDEQ-8 questionnaire.	
6.7	Subjective comfort	Subjective comfort scores using a vertical VAS scale will be recorded for the following for each lens (OD and OS):  Comfort just after lens application over the two week period  Comfort just before lens removal over the two week period	
6.8	LogMAR visual acuity & over-refraction	Distance high contrast visual acuity will be measured for each eye and binocularly before and after over-refraction. The acuity will be recorded to the nearest letter.	Eurolens Research SOP # 12a
6.9	Lens fitting and surface assessment	Lens fit will be recorded for each of the following criteria: horizontal centration, vertical centration, movement and coverage.  The lens surface will be recorded according to the following integer scales: lens deposits (0-2), deposit degree (0-4), lens debris (0-4) and lens wettability (0-4).	Eurolens Research Grading Scale (lens fit and surface assessment)
6.10	Lens removal	Lenses will be removed and discarded.	

**Clinical Study Protocol**  
**Johnson & Johnson Vision Care, Inc.**

Visit 6: Treatment 3 Follow-Up (after two weeks)			
Step	Procedure	Details	
6.11	Confocal microscopy	
Confocal microscopy will be undertaken in the following areas:
 
OD and OS Central upper lid margin
 
OD and OS Central lower lid margin
 
A number of images will be undertaken across the central lid area. Image analysis will be subsequently undertaken in order to determine the number of white blood cells.
 
N.B. This will only occur for subjects who are classified as asymptomatic or symptomatic with the CLDEQ-8.
	Eurolens Research SOP #53
6.12	Slit lamp biomicroscopy	Grades will be scored to the nearest 0.1 in the best judgment of the investigator using Efron Grading Scales.	Eurolens Research SOP #13
6.13	Exit Visual Acuity	Record distance high contrast LogMAR visual acuity (OD, OS and OU) with their with their refractive correction from Part 1, Visit 1 (or habitual spectacles) in place.	Eurolens Research SOP # 12a
6.14	End of Visit 6 and Instructions	Subjects will be asked to return for Visit 7 between 2 and 180 days from Visit 6, and may resume use of their habitual contact lenses until then. Subjects should be asked NOT to wear their lenses to Visit 7.	

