#### **1.2. Intended Use of Investigational Products**

The lenses will be used as indicated i.e. for daily wear, daily disposable use. Each lens type will be worn bilaterally for a two-week period and then followed up with an additional single study day. Subjects will be encouraged to wear the lenses for 12-14 hours during the two-week wear period and then for  $14 \pm 2$  hours on the ensuing study single visit day.

Only subjects who are classified as asymptomatic or symptomatic will go on to wear the second lens type (O1D). Asymptomatic subjects are defined as those with a CLDEQ-8 score less or equal to 10 and symptomatic subjects are defined as those with a CLDEQ-8 score of more than or equal to 20.

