#### **PART 2: VISITS 5 AND 6**

This will be a repeat of Part 1, Visits 1 and 2 but will use the O1D lens. Regardless of subjects' classification by the CLDEQ-8, all subjects will move on to Part 2, Visits 7 and 8.

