#### **PART 2: VISITS 7 AND 8**

This will be a repeat of Part 1, Visits 3 and 4 using the O1D lens. CLDEQ-8 classification with O1D does not affect participation in Part 2.

N.B. If a subject changes their habitual lens type during the study this will not affect their participation in subsequent visits.

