**Clinical Study Protocol**  
**Johnson & Johnson Vision Care, Inc.**

Visit 2: Treatment 1 Follow-Up (after two weeks)		
Step	Procedure	Details
2.7	Subjective comfort	
Subjective comfort scores using a vertical VAS scale will be recorded for the following for each lens (OD and OS):
 
Comfort just after lens application over the two week period
 
Comfort just before lens removal over the two week period

2.8	LogMAR visual acuity & over-refraction	Distance high contrast visual acuity will be measured for each eye and binocularly before and after over-refraction.
2.9	Lens fitting and surface assessment	
Lens fit will be recorded for each of the following criteria: horizontal centration, vertical centration, movement and coverage.
 
The lens surface will be recorded according to the following integer scales: lens deposits (0-2), deposit degree (0-4), lens debris (0-4) and lens wettability (0-4).

2.10	Lens removal	Lenses will be removed and discarded.
2.11	Confocal microscopy (ONLY subjects who are classified as asymptomatic or symptomatic)	
Confocal microscopy will be undertaken in the following areas:
 
OD and OS Central upper lid margin
 
OD and OS Central lower lid margin
 
A number of images will be undertaken across the central lid area. Image analysis will be subsequently undertaken in order to determine the number of white blood cells.

2.12	Slit lamp biomicroscopy	
Grades will be scored to the nearest 0.1 in the best judgment of the investigator using Efron Grading Scales.
 
N.B. For subjects who are NOT classified as asymptomatic or symptomatic slit lamp biomicroscopy will take place as part of the final evaluation form.

2.13	Continuance	
For a subject to continue on the study they must meet the following criteria:
 
Their CLDEQ-8 score must be either <math>\leq 10</math> (to be classified as asymptomatic)

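### Step 6.11 does not say which CLDEQ-8 score limits Part 2 confocal imaging; read as the Visit 6 score, it would leave score-dependent gaps in Part 2 white blood cell data

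*Combined protocol and SAP*

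**What the plan says.** Section 7.2, Part 2, Visit 6, step 6.11 schedules confocal microscopy of both lid margins in both eyes and adds: "This will only occur for subjects who are classified as asymptomatic or symptomatic with the CLDEQ-8". No visit is named. Step 6.6 of the same visit reads "Subjects will complete the CLDEQ-8 questionnaire", so by step 6.11 each subject has two scores: one from Visit 2 on the first lens and one from Visit 6 on Acuvue Oasys 1-Day (O1D).

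The matching Part 1 step, 2.11, is headed "Confocal microscopy (ONLY subjects who are classified as asymptomatic or symptomatic"). It relies on the CLDEQ-8 completed at that visit, in step 2.6.

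On entry to Part 2, Section 1.2 says: "Only subjects who are classified as asymptomatic or symptomatic will go on to wear the second lens type (O1D"). The classes are a score of 10 or less and a score of 20 or more, so 11 to 19 is unclassified.

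Section 4.1 says of Visits 5 and 6: "Regardless of subjects' classification by the CLDEQ-8, all subjects will move on to Part 2, Visits 7 and 8". Of Visits 7 and 8 it says: "CLDEQ-8 classification with O1D does not affect participation in Part 2".

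**The concern.** A site following step 2.11 in Part 1 would naturally treat step 6.11 the same way: score the questionnaire just completed and skip imaging for anyone at 11 to 19. Visit 6 is the only Part 2 confocal session in Table 3, so a skipped image cannot be recovered later.

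Three planned analyses use Part 2 WBC:

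- the Part 2 comparison of symptomatic with asymptomatic subjects (Section 2.3, Part 2 hypothesis 5; Section 14.7);
- the Part 2 correlation of WBC with comfort, part of the secondary hypothesis (Section 14.6);
- the correlation of change in CLDEQ with change in each of the five measures (Section 14.7, item 2).

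The third is the most exposed. The Visit 6 CLDEQ-8 is one of the two scores that make up the change in CLDEQ, so missingness would be set by a component of one of the correlated variables. That is selection, and enrolling more subjects does not remove it.

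**Working it through.** **Which reading has any effect**

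| Score meant by the note | Who is excluded at Visit 6 |
|---|---|
| Visit 2 (Part 1 class) | Nobody: only scores of 10 or less, or 20 or more, enter Part 2 |
| Visit 6 (O1D score) | Everyone scoring 11 to 19 on O1D |

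**Who would be lost on the second reading.** Each lost subject began at 10 or less, or at 20 or more, and ended at 11 to 19. The change can be as small as 1 point (20 to 19). A subject who crosses from one class to the other has moved at least 20 − 10 = 10 points and is still imaged. The filter therefore acts on the band of the Visit 6 score, not on the amount of change. The documents do not allow the direction of any distortion in the correlation to be determined.

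**Whether the missing-data plan would catch it.** Section 14.9 does not impute in the main analysis. Its multiple-imputation sensitivity analysis is triggered by subject dropout above 15%. A subject who attends every visit but has one procedure skipped is not a dropout, so these gaps do not count toward the trigger.

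**Illustrative loss of power for the between-strata comparison**

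Inputs: 27 per stratum (Section 14.2); mean ratio φ and CV from Table 14; one-sided 5% (Section 14.5, WBC). The method is a t-test on the ratio of lognormal means:

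- σ = √ln(1 + CV²)
- noncentrality = ln φ / (σ√(1/n₁ + 1/n₂)), with n₁ + n₂ − 2 degrees of freedom

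Reproducing Table 14 at φ = 1.5 and CV = 0.65: σ = √ln(1.4225) = 0.594; noncentrality = 0.405 / (0.594 × √(2/27)) = 2.51; 52 degrees of freedom; power 79.7%, against 80% stated. At φ = 2.0 the method gives 91.5% (CV 1.0) and 81.1% (CV 1.3), against 92% and 81%. All nine cells agree to within a point. A two-sided 5% test gives 69.3%, 85.1% and 71.0% for these three cells and does not reproduce the table.

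The share scoring 11 to 19 is not in the documents, so it is varied as an assumption. With equal loss in both strata:

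| Loss | n per stratum | φ 1.5, CV 0.65 | φ 2.0, CV 1.3 |
|---|---|---|---|
| 0% | 27 | 79.7% | 81.1% |
| 10% | 24 | 75.4% | 76.8% |
| 20% | 22 | 72.0% | 73.5% |
| 30% | 19 | 66.3% | 67.8% |
| 40% | 16 | 59.6% | 61.1% |
| 50% | 14 | 54.6% | 56.0% |

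If only symptomatic subjects are lost, power at φ 1.5 and CV 0.65 is 75.8% for a 20% loss (27 + 22) and 65.3% for a 50% loss (27 + 14).

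**The case against.** The best defence is that the note is a harmless carry-over. Section 4.1 describes Visits 5 and 6 as repeating Visits 1 and 2, group membership is fixed after Visit 2, and where the protocol means the second-lens score it can say so, as Section 4.1 does by naming O1D. Read that way the note excludes nobody. This stands as a possible reading. It does not remove the problem, because the other reading is the one the site has already applied at step 2.11.

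A reader might infer that step 6.11 flatly contradicts Section 4.1. The documents do not go that far. Section 4.1 speaks of moving on to Visits 7 and 8 and of participation, and does not mention imaging. A subject who misses one procedure at Visit 6 and attends the later visits satisfies both sentences literally. The two are in tension, no more.

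A reader might also take the mark without a condition in Table 3 as proof that everyone is to be imaged at Visit 6. It is not: Table 3 carries the same mark at Visit 2, where step 2.11 restricts imaging.

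The power figures are hypothetical. Table 14 was built for the Part 1 primary hypothesis, and no power is stated for Part 2. Section 14.7 also does not say whether the Part 2 strata are the Part 1 or the O1D classes. If they are the O1D classes, subjects at 11 to 19 belong to neither stratum and would leave that comparison whatever step 6.11 says. Both correlations would still lose their WBC values.

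**Conclusion.** The concern holds conditionally. The note is ambiguous, and the only reading under which it does anything makes Part 2 WBC missing according to the Visit 6 CLDEQ-8, with no means of recovery and no planned analysis that would be triggered by it. The main harm is selection in the change-on-change correlation. Next is a thinner WBC–comfort correlation in Part 2. The between-strata comparison is affected by step 6.11 only if the Part 2 strata are the Part 1 classes.

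For that comparison, power falls from about 80% with no loss to about 55% with half of each stratum lost. This rests on an assumed share and on Part 1 assumptions, so it illustrates scale and predicts nothing.

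It is tempting to say that the note removes exactly the subjects whose symptoms changed. That is not so: subjects who cross fully between classes, and those who change within a class, are still imaged. The Part 1 primary analyses are unaffected. The exposure is confined to secondary and other hypotheses.

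**What to change.** Delete the N.B. in step 6.11, or replace it with a statement that imaging is performed for all subjects attending Visit 6. In Section 14.7, state that the Part 2 strata are those assigned at Part 1, Visit 2, or state otherwise if the O1D classes are intended.

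The cost is two wording changes, plus confocal imaging for the subjects who would otherwise have been skipped, at a visit where the procedure is already scheduled.

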**PART 2, VISIT 7**

Visit 7 will take place in the morning and subjects MUST attend without lenses *in situ*. If possible, subjects should not wear lenses for 24 hours prior to the study visit in order to reduce the risk of biomicroscopic signs being a cause of being unable to continue on the study.

If subjects attend wearing their own lenses, this visit should NOT go ahead. The visit can still go ahead if the subject has worn their habitual lenses in the 24 hours prior to the visit.

Visit 7: Baseline			
Step	Procedure	Details	
7.1	Adverse Events and Concomitant Medications Review	Review any changes to the subject's medical history or concomitant medications from the previous study visit. Record any changes, and any adverse events.	

**Clinical Study Protocol**  
**Johnson & Johnson Vision Care, Inc.**

Visit 7: Baseline			
Step	Procedure	Details	
7.2	Subjective comfort	Subjective comfort scores using a vertical VAS scale will be recorded for each eye separately before lens application.	
7.3	Entrance Visual Acuity	Record distance high contrast LogMAR visual acuity (OD, OS and OU) with their refractive correction from Part 1 (or habitual spectacles), Visit 1 in place.	Eurolens Research SOP # 12a
7.4	Tear meniscus height	The OD lower tear meniscus will be imaged using the OCT.  Three images will be taken.	Eurolens Research SOP # 58
7.5	Non-invasive tear break-up time	OD tear film break up time will be measured using the Medmont topographer  Three measurements will be undertaken.	Eurolens Research SOP # 16
7.6	Tear film osmolarity	OD osmolarity measured using the Tearlab.  Two measurements will be undertaken.	Eurolens Research SOP # 52
7.7	Tear sample collection	OD; 2 $\mu$ l tear sample will be collected using a glass capillary tube before application of any dyes to the ocular surface.  Tears will be collected over a maximum period of 15 minutes.	Eurolens Research SOP # 57
7.8	Slit lamp biomicroscopy (white light only)	Grades will be scored to the nearest 0.1 in the best judgment of the investigator using Efron Grading Scales for both eyes.  OS: NO LID EVERSION	Eurolens Research SOP #13
7.9	Continuance	If any slit lamp findings are Efron Grade 3 or greater (e.g. corneal oedema, corneal neovascularization, tarsal abnormalities, conjunctival injection) or < Efron Grade 3 which in the investigator's opinion would contraindicate contact lens wear, the subject may not continue at this time.  If in the opinion of the investigator the subject may be eligible at a later date, the subject may	

**Clinical Study Protocol**  
**Johnson & Johnson Vision Care, Inc.**

Visit 7: Baseline		
Step	Procedure	Details
		be brought in for up to ONE additional visit of this type.

Visit 7: Treatment 4 Lens Fitting and dispensing		
Step	Procedure	Details
7.10	Ocular surface and lid margin staining photography and grading	
OS ONLY: Sodium fluorescein will be added to the ocular surface and the following will be graded using Efron scales: corneal and bulbar conjunctival staining.
 
OS ONLY: Lissamine green will then be added to the ocular surface and photographs of the upper and lower lid margin staining will be taken. These images will be used to subjectively grade lid margin staining at the time of the visit and for subsequent automated image analysis.
 
OS: after all lissamine green assessments have been completed, the eyelid will be everted and the palpebral conjunctiva will be graded using Efron Grading scales.

7.11	Lens application	
An Acuvue Oasys 1-Day contact lens will be applied to each eye (lens selection based on BVP/base curve worn between Part 2, Visits 1-2). BVP and lot number will be recorded. If a lens is damaged, a Product Quality Complaint Form will be completed. The lens will be stored in a labeled vial with unpreserved saline, and clearly differentiated from any other lenses.
 
Lenses will settle for 5 minutes

7.12	Subjective comfort	Subjective comfort scores for each lens (OD and OS) separately using a vertical VAS scale will be recorded.
7.13	LogMAR visual acuity & over-refraction	Distance high contrast visual acuity will be measured for each eye and binocularly before and after over-refraction. The acuity will be recorded to the nearest letter for each eye.

**Clinical Study Protocol**  
**Johnson & Johnson Vision Care, Inc.**

Visit 7: Treatment 4 Lens Fitting and dispensing			
Step	Procedure	Details	
		
If there is an over-refraction of 0.50DS or more, the lenses would usually be changed. However, the final decision on this will rest with the investigator. Up to TWO power modifications are allowed.
 
If the lens is changed, the lens application, comfort and VA steps should be repeated. Any new lens should be allowed to settle for 5 minutes before comfort is recorded.
 
N.B. Minimum acceptable logMAR VA is 0.18 binocularly.
	
7.14	
Lens fitting and surface assessment
	
Lens fit will be measured using a slit lamp graticule for the following:
 
Coverage:
 
Nasal coverage  Temporal Coverage  Inferior Coverage  Superior Coverage
 
Centration:
 
Horizontal centration (by auto calculation)  Vertical centration (by auto calculation)
 
Movement in primary position
 
The lens surface will be recorded according to the following integer scales: lens deposits (0-2), deposit degree (0-4), lens debris (0-4) and lens wettability (0-4).
	
Eurolens Research SOP # 24
 
Eurolens Research Grading Scale (surface assessment)

